*** Radiation fields and doses:**

Cohort 1

- a) Post segmental mastectomy: Prone whole breast 3D-CRT or IMRT at 2.7 Gy X 15 fractions (40.50 Gy) with a concomitant boost of 0.50 Gy (7.5 Gy) to the tumor bed.
- b) Post-mastectomy: Prone whole breast 3D-CRT or IMRT at 2.7 Gy X 15 fractions (40.50 Gy) with a concomitant boost of 0.50 Gy (7.5 Gy) to the mastectomy scar on the chest wall.
- c) Post-mastectomy with expanders or final reconstruction: Prone whole breast 3D-CRT or IMRT at 2.7 Gy X 15 fractions (40.50 Gy).

Cohort 2

Either a, b, c +

- d) Level III axillary nodes and Supraclavicular nodes: 3D-CRT or IMRT at 2.7 Gy X 15 fractions (40.50 Gy) -If clinically indicated, internal mammary nodes will also be treated and a supine set up will be used.

All patients will be followed for toxicity and outcome (local and systemic recurrence, survival) In addition, patients will complete a self-assessment of QOL at baseline, completion of radiation treatment, at 45-60 day follow-up and at 2 year follow-up.

TREATMENT SCHEMA

Within a month from initiation	Week 1	Week 2	Week 3	Months 3	Months 12-24-36-48-60
simulation	RT	RT	RT	Follow up	Follow up
Patient education - baseline QOL Blood sample			QOL assessment Blood sample	QOL assessment	QOL assessment

STUDY SYNOPSIS

Patients undergoing primary systemic therapy, followed by surgery often receive post-operative radiation. While the targets treated post-operatively vary and depend on the initial and post-surgical stage, patients generally undergo 6-7 weeks of daily (Monday to Friday) post-operative radiation.

This approach is long and draining, particular in this population of breast cancer patients who often experience chemotherapy-induced fatigue. Our group has developed and tested a combined positioning and hypo-fractionated regimen of post-operative radiotherapy that may be particularly convenient and indicated for these women.

Specifically a prone set-up has enabled safe sparing of heart and lung while targeting the breast and, more recently, level III and supraclavicular nodes.

While we have extensively tested this approach in the classical adjuvant setting of breast cancer, until now we have not tested it after neo-adjuvant chemotherapy.

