2.7 Post-Operative Radiotherapy After Neo-Adjuvant Chemotherapy

Neo-adjuvant/preoperative chemotherapy is usually reserved for high-risk breast cancer patients, whether because of locally advanced stage, an inflammatory breast cancer diagnosis or aggressive tumor biology. In such settings neo-adjuvant chemotherapy is considered standard care. Alternatively, a preoperative investigational approach can be tried as part of a “window of opportunity” clinical protocol, testing the effect of a novel targeted therapy. The latter choice is commonly offered in the setting of biologically more aggressive breast cancers, like triple negative breast cancer, tumors overexpressing HER2 positivity or in oestrogen receptor-positive tumors with clinically positive nodes. The majority of patients given preoperative chemotherapy subsequently undergo a mastectomy (13). Generally these patients are offered the choice of breast reconstruction and most North American patients elect to undergo reconstructive surgery. However, nowadays approximately a third of patients treated with preoperative systemic therapy undergo breast conservation surgery (BCS).

Based on the evidence for a benefit in the adjuvant setting, radiotherapy is often offered to women treated neo-adjuvantly, after surgery. Traditionally, women are treated with a supine set up that includes the breast (or chest wall / reconstructed breast) and draining nodes, over 6-7 weeks of daily visits (Monday-Friday).

Recently, the concept that the pathological response to neoadjuvant chemotherapy might be used to exclude patients from postoperative RT or to at least reduce the fields of radiotherapy has emerged. NSABP B-51/RTOG 1304 is an Intergroup clinical trial currently exploring the effects of excluding post-operative radiation or reducing the radiotherapy fields among patients who present with involved axillary nodes (documented by fine needle aspiration or core needle biopsy) and are found to have a negative sentinel node or axillary dissection after chemotherapy. The trial

randomizes patients treated with preoperative chemotherapy and mastectomy to receive or not receive post-mastectomy chest wall and regional nodal RT. Those who have been treated with segmental mastectomy are randomized to receive post-segmental mastectomy radiation to the breast alone versus breast and regional nodal RT.

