5.0 Patient Eligibility

5.1 Inclusion Criteria

- 5.1.1** Age older than 18
- 5.1.2** Pre- or post-menopausal women with Stage I-III breast cancer
- 5.1.3** Status post neoadjuvant systemic therapy
- 5.1.4** Status post-chemotherapy breast surgery
- 5.1.5** Original biopsy-proven invasive breast cancer, excised with negative margins of at least 1 mm (patients with focally positive margin are not excluded).
- 5.1.6** Status post segmental mastectomy or mastectomy, with either negative sentinel node biopsy and/or axillary node dissection (at least 6 nodes removed).
- 5.1.7** Patient needs to be able to understand and demonstrate willingness to sign a written informed consent document

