Appendix 3 – Quality Of Life Questionnaires

Appendix 3.1 Quality of Life questionnaire used at baseline

Form QLB (01-25-2005)

Quality of Life Questionnaire - Baseline

Page 1 of 7

Patient Initials ,
Last First Middle

Patient Study ID

Participants should complete this questionnaire at baseline (after consent and prior to randomization). The first page is to be completed by a clinical staff member. Fill in the items listed on this page, print the patient's study ID at the top of pages 2 through 7 and give the questionnaire to the patient for completion. After the patient has completed the questionnaire, verify that the date has been recorded at the top of page 2.

Please administer the questionnaire at an office visit if possible. If that is not possible, mail the questionnaire to the patient, then call to ask for the patient's responses over the phone. If all efforts to administer the scheduled questionnaire fail, a B-39 QMD form should be submitted instead.

Mark Circles Like This: → ●

Institution Name / Affiliate Name

Staff Member Administering Form

Last Name

First Name

Phone

Are data amended? Yes (If yes, circle the amended items.)

Time point for this questionnaire (Do not mark in this box.)

● Baseline (after consent, before randomization)

Last week of radiation therapy
45-60 days after starting radiotherapy
Two years after adjuvant radiation therapy

This form is being filled out: (Mark one.)

By participant in doctor's office By clinical staff, on phone with participant
 By participant not in doctor's office Other

Record the participant's study ID on each of the remaining pages before giving the questionnaire to the participant.

Patient
Study ID Date this questionnaire is completed:
Month Day Year*(For example, if you were completing the questionnaire on September 8, 2004, you would write 09 08 2004 in the boxes.)*

Thank you for completing this questionnaire.

We are interested in your evaluation of your physical appearance and functioning since you have been treated for breast cancer. Please rate the following items on this four-point scale, according to your evaluation at this point in time.

	Difference between treated and untreated breast and area			
	None	Slight	Moderate	Large
1 Breast size	1	2	3	4
2 Breast texture (hardening)	1	2	3	4
3 Arm heaviness	1	2	3	4
4 Nipple appearance	1	2	3	4
5 Shoulder movement	1	2	3	4
6 Arm movement	1	2	3	4
7 Breast pain	1	2	3	4
8 Ability to lift objects	1	2	3	4
9 Fit of shirt sleeve	1	2	3	4

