By circling one (1) number per line, please indicate how much you have been bothered by each of the following problems in the past four weeks.

	Not bothered at all	A little bothered	Some- what bothered	Bothered quite a bit	Bothered very much
Breast aches	0	1	2	3	4
Breast tenderness	0	1	2	3	4
Decrease or lack of arousal on breast	0	1	2	3	4
Any other problems? (Specify below)	0	1	2	3	4

Specify other problems:

You have been treated with breast conserving therapy for breast cancer. As you know, a reason for choosing this treatment is to keep a breast that looks and feels as close to normal as possible. Your opinion concerning the appearance of your breast is valuable to us. Circle the number next to the word that best describes how your breast looks now.

1	EXCELLENT: when compared to the untreated breast or the original appearance of the breast, there is minimal or no difference in the size or shape of the treated breast. The way the breast feels (its texture) is the same or slightly different. There may be thickening, scar tissue or fluid accumulation within the breast, but not enough to change the appearance.
2	GOOD: there is a slight difference in the size or shape of the treated breast as compared to the opposite breast or the original appearance of the treated breast. There may be some mild reddening or darkening of the breast. The thickening or scar tissue within the breast causes only a mild change in the shape or size.
3	FAIR: obvious differences in the size and shape of the treated breast. This change involves a quarter or less of the breast. There can be moderate thickening or scar tissue of the skin and the breast, and there may be obvious color changes.
4	POOR: marked change in the appearance of the treated breast involving more than a quarter of the breast tissue. The skin changes may be obvious and detract from the appearance of the breast. Severe scarring and thickening of the breast, which clearly alters the appearance of the breast, may be found.

My satisfaction about the treatment and results is: (Select the phrase that best describes your satisfaction.)

Totally
satisfied

Somewhat
satisfied

Neither
satisfied nor
dissatisfied

Somewhat
dissatisfied

Totally
dissatisfied

Patient
Study ID

Before any treatment to your breast, the size of your breasts was: (Select the phrase that best describes your breast size prior to treatment.)

Larger
on left

The same on
both sides

Larger
on right

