------------------------------	------------------------------------	---------------------------------	-------------------------------

Patient Study ID

By circling one (1) number per line, please indicate how much you have been bothered by each of the following problems in the past four weeks.

	Not bothered at all	A little bothered	Some- what bothered	Bothered quite a bit	Bothered very much
Fever or shivering (shaking, chills)	0	1	2	3	4
Swelling of breast (breast feels larger)	0	1	2	3	4
Breast heaviness	0	1	2	3	4
Breast warm to touch	0	1	2	3	4
Breast skin is red	0	1	2	3	4
Breast skin is tanned	0	1	2	3	4
Breast skin or area around nipple is pale in color	0	1	2	3	4
Breast skin is flaking or peeling	0	1	2	3	4
Bleeding or fluid leakage from breast	0	1	2	3	4
Breast itching	0	1	2	3	4
Blisters on the breast (or breast skin moist and raw)	0	1	2	3	4
Coughing	0	1	2	3	4
Difficulty breathing	0	1	2	3	4
Muscle aches	0	1	2	3	4
Rib or chest wall pain	0	1	2	3	4
Infections	0	1	2	3	4
Slow healing of breast wounds	0	1	2	3	4
Visible small blood vessels (spider veins)	0	1	2	3	4
Pockmarks or puncture wounds on breast	0	1	2	3	4
Thickening of breast skin	0	1	2	3	4
Hardening of breast	0	1	2	3	4
Breast or nipple numbness	0	1	2	3	4
Sharp shooting pains or twinges in the breast	0	1	2	3	4

assessment time point	 last week RT	 day 45-60	 2 years
-----------------------	------------------------------------	---------------------------------	-------------------------------

SCL

Patient Study ID

By circling one (1) number per line, please indicate how much you have been bothered by each of the following problems in the past four weeks.

	Not bothered at all	A little bothered	Some- what bothered	Bothered quite a bit	Bothered very much
Breast aches	0	1	2	3	4
Breast tenderness	0	1	2	3	4
Decrease or lack of arousal on breast	0	1	2	3	4
Tattoos on breast placed for radiation therapy	0	1	2	3	4
Any other problems? (Specify below)	0	1	2	3	4

Specify other problems:

You have been treated with breast conserving therapy for breast cancer. As you know, a reason for choosing this treatment is to keep a breast that looks and feels as close to normal as possible. Your opinion concerning the appearance of your breast is valuable to us. Circle the number next to the word that best describes how your breast looks now.

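### Both QOL forms tell every patient she had breast-conserving therapy, although mastectomy patients are eligible in both cohorts, and no split of QOL results by surgery is planned.

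*Combined protocol and SAP*

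**What the plan says.** There is one baseline form and one follow-up form. The appearance item on the baseline form opens with "You have been treated with breast conserving therapy for breast cancer". The follow-up form, used in the last week of radiotherapy, at day 45-60 and at two years, repeats it: "You have been treated with breast conserving therapy for breast cancer. As you know, a reason for choosing this treatment is to keep a breast". The patient then circles one of four grades, from Excellent (1) to Poor (4). Neither form offers a not-applicable box, a skip or a mastectomy version for this item.

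The BCTOS block on the same forms has 22 items scored 1 to 4 under the heading "Difference between treated and untreated breast and area". They include breast size, nipple appearance, shape and elevation. Section 4.1 names the BCTOS as the cosmesis measure.

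Eligibility is wider than breast conservation. Criterion 5.1.6 accepts segmental mastectomy or mastectomy. The schema lists three surgical strata for Cohort 1, the third being "Post-mastectomy with expanders or final reconstruction", and Cohort 2 takes any of the three plus nodal fields. On the background population, Section 2.7 says that most patients given preoperative chemotherapy go on to mastectomy and that "approximately a third of patients treated with preoperative systemic therapy undergo breast conservation surgery (BCS".

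QOL is a secondary endpoint (16.1.2). Its whole analysis (16.6.2) is a pointer to the primary endpoint. The subgroup sentence in 16.6.1 concerns the primary endpoint and does not name surgery type. Section 16.3 analyses the cohorts separately, but they are divided by nodal field.

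**The concern.** A patient who has had a mastectomy is told something untrue about her treatment and asked to grade a breast on that premise. She may rate the chest wall, rate a reconstruction, circle Poor or leave the item blank. The form cannot tell these apart. Appendix 3.3 requires no missing-data form for a partly completed questionnaire, so a blank carries no recorded reason.

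The BCTOS breast-appearance items raise a related problem. After mastectomy without reconstruction, the contrast with the other breast on size, shape, nipple and elevation largely reflects the operation. With no split by surgery, a cohort's cosmesis summary would reflect who had which operation as well as how the tissue tolerated accelerated radiation. A reader could then credit or blame the radiation for a difference in surgical mix.

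**Working it through.** The plan gives no power, threshold or precision for QOL, so there is no stated figure to reproduce. The check sets the passages side by side and then illustrates the size.

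**1. Form against eligibility.** The item is written for conserved breasts, while eligibility covers segmental mastectomy, mastectomy, and mastectomy with expander or reconstruction, in both cohorts. The baseline form does have a skip box on its work-activity question, for patients not in paid work, but none on the appearance item. It also tells staff to administer it before randomization, although Section 6.3 describes a non-randomized trial. That suggests, without proving it, that the forms were carried over from another study.

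**2. How many patients.** Inputs: N = 74, 37 per cohort (16.3); conservation share s = 1/3 (Section 2.7, background population, assumed to apply here).
- Statement true: 74 × 1/3 = 24.7, about 25. Per cohort: 37 × 1/3 = 12.3, about 12.
- Statement false: 74 × 2/3 = 49.3, about 49. Per cohort: about 25.
- With s = 1/2 instead: 37 true and 37 false of 74.

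**3. Dependence on surgical mix.** Let q be the proportion rating Excellent or Good among conservation patients and m the proportion among mastectomy patients. The combined proportion is s·q + (1 − s)·m. The documents give neither q nor m; take q = 0.80 for illustration.

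| m | s = 1/3 | s = 1/2 |
|---|---|---|
| 0 | 27% | 40% |
| 0.20 | 40% | 50% |
| 0.40 | 53% | 60% |
| 0.80 | 80% | 80% |

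At m = 0.20, two cohorts with identical ratings within each surgery type would differ by 10 points (50% − 40%) purely through mix. The effect vanishes only if mastectomy patients answer as conservation patients do (m = q).

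**4. Room to worsen.** The four-level item and the BCTOS items both stop at 4. A patient without reconstruction who scores 4 at baseline cannot move further, so for her the item cannot register a radiation effect.

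**5. What is unaffected.** Of the 22 BCTOS items, 10 (3, 5, 6, 8, 9, 11, 15, 16, 17, 19) concern the arm, shoulder, lifting or sleeve fit and apply after any operation. The vitality items do not refer to the breast.

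**6. Price of restricting the four-level item.** Exact (Clopper-Pearson) 95% intervals: 6/12 gives 21% to 79%; 18/37 gives 32% to 66%.

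**The case against.** The best reply has five parts.

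- **The plan may already split by surgery.** Section 16.6.2 points to 16.6.1, which reports subgroups by radiation regimen, and the schema's regimens a, b and c follow surgery type. This does not settle it: the sentence in 16.6.1 is limited to the primary endpoint and leaves regimen undefined.
- **No pooled cosmesis score is planned.** This stands. A reader might infer that the plan commits to one, but the documents are only silent. Combining surgery types is what happens by default.
- **The four-level item is not a named measure.** This also stands. Section 4.1 and the calendar footnote name only the BCTOS and the SF-36 Vitality Scale, and the BCTOS heading does not mention conservation. The false statement therefore affects an unnamed item, and the BCTOS problem is one of applicability.
- **Baseline follows surgery.** Surgery is complete before accrual (6.1, 8.0) and the baseline form precedes radiation, so within-patient change absorbs part of the surgical deficit. That rules out the tempting reading that these items measure only the operation. But no change analysis is specified, the limit on worsening remains, and patients with expanders may enter before final reconstruction (8.0), so later surgery could move their two-year scores.
- **One third is not a trial figure.** Correct. This trial selects on indication for radiotherapy and on nodal involvement, and its mix could differ, including between cohorts.

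**Conclusion.** The concern holds in limited form. The forms misdescribe the treatment of every mastectomy patient, and nothing in the analysis section separates her answers from those of conservation patients. Cohort-level summaries of the four-level item and of the BCTOS breast-appearance items would depend partly on surgical mix. After mastectomy without reconstruction, some of these items may already be at their worst level before radiation starts.

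The figure of about 49 of 74 rests wholly on applying the Section 2.7 background share to this trial. The percentages in the mix illustration rest on assumed response rates.

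A reader might conclude that the cosmesis results are uninterpretable, or wrong for both surgical groups. The documents do not support that. Segmental-mastectomy answers remain valid, and reconstructed patients can still rate size, shape and texture. The arm and shoulder items and the vitality scale apply to everyone. The primary dermatitis endpoint is untouched. This is a correctable defect in a secondary endpoint.

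**What to change.** 1. On both forms, add a not-applicable (mastectomy) box to the four-level appearance item, and summarise that item in segmental-mastectomy patients only.
2. In 16.6.2, state that the BCTOS breast-appearance items are reported separately for segmental mastectomy, mastectomy without reconstruction, and mastectomy with expander or reconstruction, as change from the post-surgery, pre-radiation baseline. Keep reconstructed patients' data: restricting these items to segmental mastectomy would discard usable answers.

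The cost is one box on two forms and a short addition to 16.6.2. The validated scales stay as they are. Surgery type is already needed to assign the boost, so the reporting rule can also be applied to forms already collected. The downside is precision: with about 12 conservation patients per cohort under the one-third assumption, intervals would be wide, but each would describe a defined group.

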Appendix 3.2 Quality of Life questionnaire used for follow-up visits

Form QLF(01-25-2005)

Quality of Life Questionnaire - Follow-up

Page 1 of 6

Patient Initials ,
 Last First Middle

Patient Study ID

For patients who receive both radiation and chemotherapy, this should be completed at day 45-60 following start of radiation and at 2-year follow-up.

Patients who experience a documented cancer recurrence or second primary cancer are not expected to complete questionnaires after that event. Patients who discontinue therapy for other reasons are expected to complete all the quality of life assessments.

The first page is to be completed by a clinical staff member. Fill in the items listed on this page, print the patient's study ID at the top of pages 2 through 6 and the assessment time point at the bottom of pages 1 through 6 and give the questionnaire to the patient for completion. After the patient has completed the questionnaire, verify that the date has been recorded at the top of page 2.

Please administer the questionnaire at an office visit if possible. If that is not possible, mail the questionnaire to the patient, then call to ask for the patient's responses over the phone. If all efforts to administer the scheduled questionnaire fail, a B-39 QMD form should be submitted instead.

Institution Name / Affiliate Name		
/		
Staff Member Administering Form		
Last Name	First Name	Phone
Are data amended?  Yes (If yes, circle the amended items.)		
This form is being filled out: (Mark one.)		
 By participant in doctor's office  By clinical staff, on phone with participant  By participant not in doctor's office  Other		

Mark Circles Like This: → ●

assessment time point	 last week RT	 day 45-60	 2 years
-----------------------	------------------------------------	---------------------------------	-------------------------------

Record the assessment time point and participant's Study ID on each of the remaining pages before giving the questionnaire to the participant.

Patient Study ID Date this questionnaire is completed:
Month Day Year*(For example, if you were completing the questionnaire on September 8, 2004, you would write 09 08 2004 in the boxes.)*

Thank you for completing this questionnaire.

We are interested in your evaluation of your physical appearance and functioning since you have been treated for breast cancer. Please rate the following items on this four-point scale, according to your evaluation at this point in time.**Difference between treated and untreated breast and area**

	None	Slight	Moderate	Large
1 Breast size	1	2	3	4
2 Breast texture (hardening)	1	2	3	4
3 Arm heaviness	1	2	3	4
4 Nipple appearance	1	2	3	4
5 Shoulder movement	1	2	3	4
6 Arm movement	1	2	3	4
7 Breast pain	1	2	3	4
8 Ability to lift objects	1	2	3	4
9 Fit of shirt sleeve	1	2	3	4
10 Breast tenderness	1	2	3	4
11 Shoulder stiffness	1	2	3	4
12 Breast shape	1	2	3	4
13 Breast elevation (how high the breast is)	1	2	3	4
14 Scar tissue	1	2	3	4
15 Shoulder pain	1	2	3	4
16 Arm pain	1	2	3	4
17 Arm swelling	1	2	3	4
18 Breast swelling	1	2	3	4
19 Arm stiffness	1	2	3	4
20 Fit of bra	1	2	3	4
21 Breast sensitivity	1	2	3	4
22 Fit of clothing	1	2	3	4

assessment time point last week RT day 45-60 2 years

Patient Study ID

These questions are about how you feel and how things have been with you during the past 4 weeks. For each question, please give the one answer that comes closest to the way you have been feeling.

How much of the time during the past 4 weeks...

	All of the time	Most of the time	Some of the time	A little of the time	None of the time
1. Did you feel full of life?	1	2	3	4	5
2. Did you have a lot of energy?	1	2	3	4	5
3. Did you feel worn out?	1	2	3	4	5
4. Did you feel tired?	1	2	3	4	5

5. Rate your pain at its worst in the past four weeks. (Circle one number.)

0	1	2	3	4	5	6	7	8	9	10
---	---	---	---	---	---	---	---	---	---	----

No pain

Pain as bad as you can imagine

6. Rate your pain at its least in the past four weeks. (Circle one number.)

0	1	2	3	4	5	6	7	8	9	10
---	---	---	---	---	---	---	---	---	---	----

No pain

Pain as bad as you can imagine

7. Rate your pain on average in the past four weeks. (Circle one number.)

0	1	2	3	4	5	6	7	8	9	10
---	---	---	---	---	---	---	---	---	---	----

No pain

Pain as bad as you can imagine

8. Rate how much pain you have right now. (Circle one number.)

0	1	2	3	4	5	6	7	8	9	10
---	---	---	---	---	---	---	---	---	---	----

No pain

Pain as bad as you can imagine

9. Are you currently receiving treatments or taking medications for your pain?

Circle one: Yes No

assessment time point	 last week RT	 day 45-60	 2 years
------------------------------	------------------------------------	---------------------------------	-------------------------------

Patient Study ID

By circling one (1) number per line, please indicate how much you have been bothered by each of the following problems in the past four weeks.

	Not bothered at all	A little bothered	Some- what bothered	Bothered quite a bit	Bothered very much
Fever or shivering (shaking, chills)	0	1	2	3	4
Swelling of breast (breast feels larger)	0	1	2	3	4
Breast heaviness	0	1	2	3	4
Breast warm to touch	0	1	2	3	4
Breast skin is red	0	1	2	3	4
Breast skin is tanned	0	1	2	3	4
Breast skin or area around nipple is pale in color	0	1	2	3	4
Breast skin is flaking or peeling	0	1	2	3	4
Bleeding or fluid leakage from breast	0	1	2	3	4
Breast itching	0	1	2	3	4
Blisters on the breast (or breast skin moist and raw)	0	1	2	3	4
Coughing	0	1	2	3	4
Difficulty breathing	0	1	2	3	4
Muscle aches	0	1	2	3	4
Rib or chest wall pain	0	1	2	3	4
Infections	0	1	2	3	4
Slow healing of breast wounds	0	1	2	3	4
Visible small blood vessels (spider veins)	0	1	2	3	4
Pockmarks or puncture wounds on breast	0	1	2	3	4
Thickening of breast skin	0	1	2	3	4
Hardening of breast	0	1	2	3	4
Breast or nipple numbness	0	1	2	3	4
Sharp shooting pains or twinges in the breast	0	1	2	3	4

assessment time point	 last week RT	 day 45-60	 2 years
-----------------------	------------------------------------	---------------------------------	-------------------------------

SCL

Patient Study ID

By circling one (1) number per line, please indicate how much you have been bothered by each of the following problems in the past four weeks.

	Not bothered at all	A little bothered	Some- what bothered	Bothered quite a bit	Bothered very much
Breast aches	0	1	2	3	4
Breast tenderness	0	1	2	3	4
Decrease or lack of arousal on breast	0	1	2	3	4
Tattoos on breast placed for radiation therapy	0	1	2	3	4
Any other problems? (Specify below)	0	1	2	3	4

Specify other problems:

You have been treated with breast conserving therapy for breast cancer. As you know, a reason for choosing this treatment is to keep a breast that looks and feels as close to normal as possible. Your opinion concerning the appearance of your breast is valuable to us. Circle the number next to the word that best describes how your breast looks now.

1	EXCELLENT: when compared to the untreated breast or the original appearance of the breast, there is minimal or no difference in the size or shape of the treated breast. The way the breast feels (its texture) is the same or slightly different. There may be thickening, scar tissue or fluid accumulation within the breast, but not enough to change the appearance.
2	GOOD: there is a slight difference in the size or shape of the treated breast as compared to the opposite breast or the original appearance of the treated breast. There may be some mild reddening or darkening of the breast. The thickening or scar tissue within the breast causes only a mild change in the shape or size.
3	FAIR: obvious differences in the size and shape of the treated breast. This change involves a quarter or less of the breast. There can be moderate thickening or scar tissue of the skin and the breast, and there may be obvious color changes.
4	POOR: marked change in the appearance of the treated breast involving more than a quarter of the breast tissue. The skin changes may be obvious and detract from the appearance of the breast. Severe scarring and thickening of the breast, which clearly alters the appearance of the breast, may be found.

assessment time point last week RT day 45-60 2 years

Patient Study ID

My satisfaction about the treatment and results is: (Select the phrase that best describes your satisfaction.)

Totally satisfied

Somewhat satisfied

Neither satisfied nor dissatisfied

Somewhat dissatisfied

Totally dissatisfied

Before any treatment to your breast, the size of your breasts was: (Select the phrase that best describes your breast size prior to treatment.)

Larger on left

The same on both sides

Larger on right

The size of your breasts now is: (Select the phrase that best describes your breast size now.)

Larger on left

The same on both sides

Larger on right

Thank you for completing this questionnaire!

assessment time point last week RT day 45-60 2 years

